Visit Window			$\pm 3d$	$\pm 3d$	$\pm 3d$	$\pm 3d$	± 3d	+ 7d	$\pm 7d$	± 7d
Pregnancy test ¹	Х	Х				Х	Х		Х	
Blood sample for determination of BRCA status via Myriad ^{m,n}	Х									
Blood sample for disease specific marker (CA-125) °		Х				Х	Х	Х		
Tumor Assessment (CT or MRI according to RECIST v1.1)	X ^p	st (± 1	Every 8 weeks (± 1 week) from receipt of first dose of study drug (Visit 2) for 48 weeks and every 12 weeks (± 1 week) thereafter until PD has been determined by the Investigator according to RECIST v1.1 criteria (including confirmatory RECIST scan).							
Adverse events (continuous from the time of informed consent) ^q	Х	Х	Х	Х	Х	Х	Х	Х	Х	
Concomitant medications including blood transfusions	Х	Х	Х	Х	Х	Х	Х	Х	Х	
Olaparib dispensed/returned r		Х				Х	Х	Х		

Table 6

Study Plan - On Study Treatment and Discontinuation

Visit Number	1	2	3	4	5	6	Subsequent on treatment visits every 4 weeks ^a Tumor assessment visits every 8 or 12 weeks ^b Visit No. 7 onwards	Study treatment discontinued ^c	Follow-up 30 days after last dose of study medication ^d	Overall Survival Follow-up °
Day	-28 to -1	1	8	15	22	29	Day 1 of next visit period ^f			4
Visit Window			± 3d	+ 7d	± 7d	± 7d				
Subsequent cancer therapy following discontinuation of study treatment ^s									Х	
Blood sample for pharmacogenetics (mandatory) ^t		X								-
Tumor sample (mandatory) ^m , n,u,v	Х									
CCI										
The second secon										
										X

a. Visit to take place on Day 1 of a 4-week visit period up to 52 weeks (if not progressed and still on treatment), then on Day 1 of a 12-week visit period relative to date of enrollment until PD (RECIST v1.1).
b. Follow-up assessments will be performed at the end of every 8 weeks (± 1 week) up to 48 weeks, then every 12 weeks (± 1 week) relative to date of enrollment until PD (RECIST v1.1).
b. Follow-up assessments will be performed at the end of every 8 weeks (± 1 week) up to 48 weeks, then every 12 weeks (± 1 week) relative to date of enrollment until PD (RECIST v1.1).

Date 10 October 2017

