- chest or upper abdomen lymphadenopathy at baseline), abdomen, and pelvis with any other regions imaged at baseline where disease was present. Any other sites at which new disease is suspected should also be appropriately imaged. Subjects must be followed until RECIST PD. If an unscheduled assessment was performed and the subject has not progressed, every attempt should be made to perform the subsequent assessments at their scheduled visits. Subjects who are determined to have PD according to RECIST v1.1 criteria (including confirmatory RECIST scan) by the Investigator may have additional scans performed per the site's standard of care. Scans will be collected through disease progression.
- c. Subjects should be discontinued from study treatment if they have objective radiological disease progression according to RECIST v1.1 (see Appendix G) and complete the Study Treatment Discontinuation Visit as per the study plan.
- d. During the follow-up period, subjects will be followed for PFS (CA-125 and radiographic evidence of progression per site standards) until database lock/end of study, and assessed for overall survival.
- e. Assessments for survival should be made every 12 weeks (± 1 week) following disease progression. Survival information may be obtained via telephone or email contact with the subject's family, or by contact with the subject's current physician.
- f. Visit 7 equals Day 57 (Week 8), then Visit 8 equals Day 85 (Week 12), etc.
- g. Informed consent for pre-screening will be taken specifically for myChoice[®] HRD (central Myriad HRD tumor) and BRACAnalysis CDx[®] (gBRCA testing). A separate informed consent needs to be signed to begin study procedures for the overall study.
- All inclusion/exclusion criteria including history of blood transfusion within previous 120 days from informed consent and the reasons (e.g., bleeding or myelosuppression).
- Height will only be recorded at screening. Temperature and weight only required if clinically indicated. Physical examination should be performed according to the schedule; after the baseline assessment it is not necessary to record the details on an eCRF unless related to an adverse event/SAE. Any clinically significant changes should be recorded as adverse events.
- j. The ECG at screening should be performed within 7 days prior to starting the study treatment. Electrocardiograms should be performed once the subject has been in the supine position for at least 5 minutes in each case.

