- k. Coagulation tests are only required if clinically indicated. For a list of all required laboratory tests, please refer to Section 5.2.1. All enrolled subjects will have safety blood samples taken weekly during the first month on treatment followed by monthly assessments until discontinuation of study treatment. Safety blood samples will be taken at the 30-day Follow-up Visit as well.
- 1. Women of childbearing potential must have a negative urine or serum pregnancy test within 28 days prior to starting treatment and a confirmatory test on Day 1 before initiating olaparib treatment; and at the timepoints shown in Table 6 during study treatment, and at the 30 day follow up visit. Pregnancy testing for women of childbearing potential should be conducted at regular intervals (eg, monthly). If results are positive, the subject is ineligible/must be discontinued from the study.
- m. Subjects with an unknown gBRCA status will have their blood and tumor tested with the myChoice[®] HRD and BRACAnalysis CDx[®] in parallel at pre-screening (if consented) or at screening, if not previously performed by Myriad during pre-screening.
- n. Subjects with known gBRCA status from the local laboratory must provide a blood and tumor sample at screening for confirmatory purposes. Their involvement in the study will not be affected by the result of the Myriad test.
- CA-125 will be tested at baseline and every month thereafter until objective disease progression, based on progressive serial elevation of serum CA-125 according to the modified GCIG criteria. Samples should be taken pre-dose at Visit 2.
- p. RECIST assessments will be performed using CT/MRI of the chest, abdomen, and pelvis, with other regions as clinically indicated for the assessment of disease, no more than 28 days prior to study treatment start and as close as possible to the start of study treatment. A CT examination with intravenous contrast media administration is the preferred method. An MRI should be used where CT is not feasible or it is medically contraindicated.

Date 10 October 2017

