4.3 Follow-up period

4.3.1 Follow-up 30 days after the last dose of olaparib (Follow-up Visit)

A Follow-up Visit should be conducted 30 days (\pm 7 days) after the last dose of olaparib. Any SAEs or adverse events ongoing at the time of the Study Treatment Discontinuation Visit or which have occurred during the defined 30-day follow-up period must be followed-up (in accordance with Section 6.3.1). Appropriate safety evaluations should be repeated and/or additional tests performed at any time when clinically indicated, or at the discretion of the Investigator, until resolution, unless, in the Investigator's opinion, the condition is unlikely to resolve due to the subject's underlying disease. If the subject is lost to follow-up, then this should be noted in the eCRF.

The following assessments will be performed:

- Obtain vital signs, body weight, and ECG (see Sections 5.2.3 and 5.2.4);
- Obtain sample for pregnancy test, if necessary (see Section 5.2.5.1);
- Obtain blood sample for hematology/clinical chemistry (see Section 5.2.1 and Table 8);
- Assess and record concomitant medications including blood transfusions;
- Assess subject for adverse events (continuous from time of informed consent) (see Section 6.3.1); and
- Record subsequent cancer therapy following discontinuation of study treatment.

During the follow-up period, subjects will be followed for PFS (CA-125 and radiographic evidence of progression per site standards) until database lock/end of study and assessed for OS.

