5.1 Efficacy assessments

5.1.1 CT and MRI scans tumor assessments (RECIST v1.1)

The baseline tumor assessment will be performed no more than 28 days prior to study treatment start (Visit 2) and as close as possible to study treatment start. Following the

baseline tumor assessment, subsequent tumor assessments according to RECIST v1.1 should be performed at the end of every 8 weeks (\pm 1 week) from first dose of study drug (Visit 2) for 48 weeks and every 12 weeks (\pm 1 week) (relative to the date of enrollment) thereafter until PD. If an unscheduled assessment was performed and the subject has not progressed, every attempt should be made to perform the subsequent assessments at their scheduled visits. Subjects who are determined to have PD according to RECIST v1.1 criteria (including confirmatory RECIST scan) by the Investigator may have additional scans performed per the site's standard of care. All treatment decisions will be based on the Investigator's assessment of the scans.

A copy of all tumor assessment scans will be collected by an AstraZeneca Representative through disease progression.

All subjects should have RECIST assessments until documented evidence of objective radiological progression in accordance with RECIST v1.1, irrespective of treatment decisions (i.e., RECIST follow-up until progression even if a subject discontinues study treatment prior to progression and/or receives a subsequent therapy prior to progression).

At baseline, the imaging modalities used for RECIST assessment will be CT (MRI where CT is contraindicated) scans of the chest, abdomen, and pelvis, with other regions as clinically indicated for the assessment of disease. Follow-up CT or MRI assessments (per RECIST v1.1) will be by chest (in those subjects with disease in the chest or upper abdomen lymphadenopathy at baseline), abdomen, and pelvis, with any other regions imaged at baseline where disease was present. Any other sites at which new disease is suspected should also be appropriately imaged. The methods of assessment of tumor burden used at baseline must be used at each subsequent follow-up assessment. A CT examination with intravenous contrast media administration is the preferred method. An MRI should be used where CT is not feasible or it is medically contraindicated. For brain lesion assessment, MRI is the preferred method. Subjects must be followed-up until RECIST disease progression.

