8.4.3.4 Progression-free survival

Progression-free survival is defined as the time from the date of first dose of olaparib until the date of objective radiological disease progression (Investigator assessed via RECIST v1.1) or death (by any cause in the absence of disease progression) regardless of whether the subject withdraws from therapy or receives another anticancer therapy prior to disease progression. Subjects who have not progressed or died at the time of analysis will be censored at the time of the latest date of assessment from their last evaluable efficacy assessment. However, if the subject progresses or dies after 2 or more missed visits, the subject will be censored at the time of the latest evaluable assessment. Given the scheduled visit assessment scheme, 2 missing visits will equate to more than 18 weeks (or 26 weeks after 1 year) since the previous RECIST v1.1 assessment, allowing for early and late visits. If the subject has no evaluable visits or does not have a baseline assessment, they will be censored at Day 1 unless they die within 2 visits of baseline (18 weeks allowing for visit window).

The PFS time will always be derived based on scan/assessment dates and not visit dates. Assessments/scans contributing towards a particular visit may be performed on different dates. The following rules will be applied:

- Date of progression will be determined based on the earliest of the assessment/scan dates of the component that triggered the progression.
- When censoring a subject for PFS, the subject will be censored at the latest of the assessment/scan dates contributing to a particular overall visit assessment.

Overall visit assessments will be determined for each assessment (scheduled or unscheduled) and will contribute to the derivation of PFS.

Objective radiological progression is defined as at least a 20% increase in the sum of the diameters of the TLs (compared to previous minimum sum) and an absolute increase of > 5 mm, an overall non-TL assessment of progression, or a new lesion.

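### For subjects who stop olaparib before RECIST progression, Section 4.3.1 and Table 6 footnote d leave progression follow-up to site practice, against Sections 3.9.1 and 5.1.1 and the rest of Table 6; PFS and DoR events could be dated late or censored

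*Protocol*

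**What the plan says.** The protocol gives two rules for the same subjects, those who stop olaparib before objective progression.

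**Local follow-up.** Section 4.3.1: "subjects will be followed for PFS (CA-125 and radiographic evidence of progression per site standards) until database lock/end of study". Table 6 footnote d, attached to the 30-day follow-up column, says the same: "followed for PFS (CA-125 and radiographic evidence of progression per site standards) until database lock/end of study". Neither gives an interval or names RECIST v1.1, and both list CA-125 as evidence for PFS.

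**Fixed RECIST follow-up.** Section 5.1.1 asks for "RECIST follow-up until progression even if a subject discontinues study treatment prior to progression and/or receives a subsequent therapy prior to progression". Its calendar is 8-weekly "from first dose of study drug (Visit 2) for 48 weeks and every 12 weeks" thereafter, each with a one-week window either side. The Table 6 tumor assessment row carries the same calendar until progression, and footnote b requires follow-up to RECIST progression. Section 3.9.1 also requires RECIST v1.1 follow-up after withdrawal from olaparib, but sends the site to Section 4.3 and Table 6 for the plan, where the site-standard wording stands.

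**Analysis.** Section 8.4.3.4 counts progressions after withdrawal from therapy or after another therapy, and defines progression as objective and radiological. It adds: "if the subject progresses or dies after 2 or more missed visits, the subject will be censored at the time of the latest evaluable assessment". Two missed visits means a gap of more than 18 weeks, or 26 weeks after 1 year. Section 8.4.3.1 takes the end of response from the PFS date. Section 5.1.2 says CA-125 is not used directly to judge objective response or progression.

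**The concern.** The PFS rule presumes that everyone without progression is scanned on one calendar, on or off drug. Section 4.3.1 lets a site do otherwise without breaching the protocol. Two things could then happen to a subject who stops for toxicity or by choice. If the local interval is longer than the calendar but within the missed-visit limit, progression is found and dated late. If the interval exceeds the limit, the progression is discarded and the subject is censored at the last evaluable scan, even though the site did what Section 4.3.1 told it to do. That censoring depends on why and when the subject left treatment. Late dating and lost events both tend to lengthen PFS, and DoR inherits the error through the shared end date.

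The CA-125 wording is a second fault in the same sentence. A site could record a marker rise as a PFS event, which Section 8.4.3.4 does not allow.

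**Working it through.** **1. The plan's own limits.** Two scan intervals plus one week early and one week late:
- 8-weekly phase: 2 × 8 + 2 = 18 weeks.
- 12-weekly phase: 2 × 12 + 2 = 26 weeks.

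Both match Section 8.4.3.4, so the limits are derived from the fixed calendar. On that calendar the longest on-time gap is 12 + 2 = 14 weeks, and no progression is censored by this rule.

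**2. Assumptions for the alternative (none is in the protocol).** PFS is exponential with a 9-month median, i.e. 9 × 52.1775 / 12 = 39.13 weeks (6 and 12 months as a range). Olaparib is stopped at the week-16 scan, with local scans at a constant interval from then. 5% to 20% of subjects are marked to stop, and count only if still progression-free at week 16. Every subject is followed to an event, without the administrative data cut-off.

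**3. Intervals within the limit.** Mean delay in dating progression relative to the fixed calendar, by simulation:
- every 12 weeks: 0.9 weeks (0.7 to 1.2 over the median range), none censored;
- every 16 weeks: 3.1 weeks (2.8 to 3.5), none censored.

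The 12-week figure is small because the protocol calendar is itself 12-weekly after week 48.

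**4. Intervals beyond the limit.** A progression is censored if the preceding scan was before week 52 and the gap exceeds 18 weeks. From week 52 on, neither a 20- nor a 26-week gap exceeds 26.
- Every 20 weeks: scans at 16, 36, 56. Progressions between weeks 16 and 56 are lost: 1 − 2^(−40/39.13) = 0.51.
- Every 26 weeks: scans at 16, 42, 68. Progressions between weeks 16 and 68 are lost: 1 − 2^(−52/39.13) = 0.60.

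With medians of 12 and 6 months (52.18 and 26.09 weeks) the same formulas give 0.41 to 0.65 and 0.50 to 0.75.

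**5. Effect on a cohort.** The chance of being progression-free at week 16 is 2^(−16/39.13) = 0.753. Events lost run from 0.05 × 0.753 × 0.51 = 1.9% to 0.20 × 0.753 × 0.60 = 9.0% (9.1% by simulation).

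On the fixed calendar the last scan by week 52 is at week 48, so the 12-month Kaplan-Meier estimate is 2^(−48/39.13) = 0.427. By simulation it becomes:

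| Off-treatment interval | 5% stop early | 20% stop early |
|---|---|---|
| 12 weeks | 0.426 | 0.422 |
| 16 weeks | 0.427 | 0.427 |
| 20 weeks | 0.437 | 0.469 |
| 26 weeks | 0.437 | 0.468 |

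At 12 to 16 weeks the 12-month estimate hardly moves. It even dips slightly at 12 weeks, because that local grid happens to place a scan at week 52.

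**6. TTAP.** Section 8.4.3.5 censors only when both RECIST and CA-125 assessments have been missed. Lapsed scans alone do not trigger it, so late dating is the main effect.

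**The case against.** Most of the text favors the fixed calendar: Section 3.9.1, Section 5.1.1, the Table 6 imaging row and footnote b, against one sentence used twice. A coordinator who schedules from Table 6 meets the fixed calendar in the imaging row. That stands, and a reader who inferred that Table 6 as a whole prescribes site practice would be wrong: only footnote d does. It does not resolve the conflict, because no clause ranks the sections and Section 3.9.1 points back to Section 4.3 and Table 6.

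It may be said that the sentence concerns the period after progression. But following a subject for PFS has meaning only before progression, and Section 5.1.1 deals separately with standard-of-care scans afterwards. It may also be said that it means imaging method rather than timing. The text does not say so, and on that reading it still omits RECIST v1.1.

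The endpoints affected are secondary and the analyses descriptive, with no tests (Section 8.5). That limits the stakes. The primary ORR is little affected, except where a confirming scan falls after treatment stops.

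**Conclusion.** The contradiction stands and should be corrected. The consequence is conditional: progressions could be dated late or censored, with PFS and DoR biased upward, only in subjects who stop before progression at sites that follow Section 4.3.1. Under the assumptions above, 12-month PFS moves from about 0.43 to 0.44-0.47 at 20- to 26-week scanning. At 12 to 16 weeks the effect is a mean delay of about 1 to 3 weeks.

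Three stronger conclusions that a reader might draw are not supported. The documents do not show that events will be lost, since they give neither site intervals nor early-stop rates. A 26-week interval does not lose every event, since the limit is itself 26 weeks after 1 year. TTAP is not exposed in the same way as PFS and DoR, since its censoring needs both kinds of assessment to lapse.

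A separate and lesser inconsistency concerns CA-125 timing. A Table 6 footnote says "CA-125 will be tested at baseline and every month thereafter until objective disease progression", and Section 5.2.1.4 asks for a sample each 4-week period. Yet after week 52 visits move to a longer spacing in Table 6 footnote a, "then on Day 1 of a 12-week visit period relative to date of enrollment until PD (RECIST v1.1"), and in Section 4.2.4. It does not by itself show that TTAP will mix two sampling grids, because the monthly rule is explicit.

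**What to change.** - In Section 4.3.1 and Table 6 footnote d, replace the site-standard wording with a reference to the RECIST v1.1 schedule in Section 5.1.1 until objective progression, on or off treatment.
- In the same two places, remove CA-125 as evidence for PFS and keep it for TTAP.
- Keep the 18- and 26-week limits in Section 8.4.3.4 tied to that schedule.
- Separately, reconcile the CA-125 rule (Table 6 footnote, Section 5.2.1.4) with the visit spacing after week 52 (Table 6 footnote a, Section 4.2.4) and with follow-up after discontinuation, so that the missed-assessment rule in Section 8.4.3.5 has one stated interval to work from.

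The cost is protocol wording and notice to sites. No scan is added beyond those Section 5.1.1 already requires.

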4.3.2 Follow-up after final data cut-off for the primary endpoint analysis/end of study

After data cut-off for the primary endpoint (ORR), during the additional 12 months of follow-up, subjects will be assessed for adverse events (see Section 6.3.1.1), and assessed for survival every 3 months until the closure of the study.

At the end of the additional 12 months of survival and safety follow-up, the study will be closed. Subjects who are receiving treatment at this time can either choose to discontinue from olaparib, or where the Investigator believes subjects are gaining clinical benefit, subjects may continue to receive olaparib off study. AstraZeneca will continue to supply olaparib after completion of this study until either olaparib tablets are licensed in the US, or it is determined that the benefit-to-risk profile does not support continued development of olaparib, or the FDA has deemed the drug not approvable. In all these scenarios, AstraZeneca will work with Investigators on the proper transition of subjects to alternative therapies if possible.

4.4 Survival follow-up

All subjects who enrolled and received at least 1 dose of olaparib will be followed for survival. Subjects will be contacted to assess for survival status every 12 weeks following disease progression until death, withdrawal of consent, or study closure. Survival information may be obtained via telephone or email contact with the subject, subject's family, or by contact with the subject's current physician. The vital status of the subject can be obtained by site personnel from publicly available resources where it is possible to do so under applicable local laws.

5. STUDY ASSESSMENTS

An EDC system will be used for data collection and query handling. The Investigator will ensure that data are recorded in the eCRF as specified in the Clinical Study Protocol and in accordance with the instructions provided.

The Investigator will ensure the accuracy, completeness, and timeliness of the data recorded and of the provision of answers to data queries according to the Clinical Study Agreement. The Investigator will sign the completed eCRF. A copy of the completed eCRF will be archived at the study site.

5.1 Efficacy assessments

5.1.1 CT and MRI scans tumor assessments (RECIST v1.1)

The baseline tumor assessment will be performed no more than 28 days prior to study treatment start (Visit 2) and as close as possible to study treatment start. Following the

baseline tumor assessment, subsequent tumor assessments according to RECIST v1.1 should be performed at the end of every 8 weeks (\pm 1 week) from first dose of study drug (Visit 2) for 48 weeks and every 12 weeks (\pm 1 week) (relative to the date of enrollment) thereafter until PD. If an unscheduled assessment was performed and the subject has not progressed, every attempt should be made to perform the subsequent assessments at their scheduled visits. Subjects who are determined to have PD according to RECIST v1.1 criteria (including confirmatory RECIST scan) by the Investigator may have additional scans performed per the site's standard of care. All treatment decisions will be based on the Investigator's assessment of the scans.

A copy of all tumor assessment scans will be collected by an AstraZeneca Representative through disease progression.

All subjects should have RECIST assessments until documented evidence of objective radiological progression in accordance with RECIST v1.1, irrespective of treatment decisions (i.e., RECIST follow-up until progression even if a subject discontinues study treatment prior to progression and/or receives a subsequent therapy prior to progression).

At baseline, the imaging modalities used for RECIST assessment will be CT (MRI where CT is contraindicated) scans of the chest, abdomen, and pelvis, with other regions as clinically indicated for the assessment of disease. Follow-up CT or MRI assessments (per RECIST v1.1) will be by chest (in those subjects with disease in the chest or upper abdomen lymphadenopathy at baseline), abdomen, and pelvis, with any other regions imaged at baseline where disease was present. Any other sites at which new disease is suspected should also be appropriately imaged. The methods of assessment of tumor burden used at baseline must be used at each subsequent follow-up assessment. A CT examination with intravenous contrast media administration is the preferred method. An MRI should be used where CT is not feasible or it is medically contraindicated. For brain lesion assessment, MRI is the preferred method. Subjects must be followed-up until RECIST disease progression.

Radiological examinations performed in the conduct of this study should be retained at the site as source data.

It is important to follow the assessment schedule as closely as possible. If scans are performed outside of the scheduled visit ± 1 week window interval and the subject has not progressed, every attempt should be made to perform the subsequent scans at their scheduled time points (± 1 week).

